		APPENDIX 7: STATEMENT OF INVESTIGATOR	
		APPENDIX 8: SUB-INVESTIGATOR AGREEMENT	59

PROTOCOL SIGNATURE PAGE

The signature below constitutes the approval of this protocol entitled **A** prospective, single arm, multi-center study evaluating the short-term clinical outcomes of ventral hernias treated with OviTex® reinforced bioscaffold, and provides the necessary assurances that this trial will be conducted in compliance of all stipulations of the protocol, including all statements regarding confidentiality, and according to local legal and regulatory requirements, the Food and Drug Administration, International Conference on Harmonization Good Clinical Practice E6 (ICH-GCP), and applicable US regulatory requirements.

Investigator's Printed Name		
Investigator's Signature	Date	

STUDY SYNOPSIS

Title	A prospective, single arm, multi-center study evaluating the clinical
	outcomes of ventral hernias treated with OviTex® Permanent 1S
	reinforced bioscaffold.
Investigational Product	OviTex® Permanent 1S reinforced bioscaffold
Protocol Number	TB2016.01.01
Study Design	A prospective, single arm, multi-center study
Number of Study Sites	Up to 7
Number of Subjects	100
Study Population	Male and female subjects at least 18 years of age presenting with ventral hernia
Study Treatment	OviTex Permanent 1S reinforced bioscaffold in hernia repair
Study Objective	The study evaluates the post-operative complications and re-
	herniations following the use of OviTex® Permanent 1S reinforced
	bioscaffold in subjects with ventral hernias.
Study Endpoints	Primary endpoints:
	1. Incidence of early post-operative surgical site
	occurrences or wound related events (e.g ileus, deep or
	superficial wound infection, seroma, hematoma, wound
	dehiscence, skin necrosis, fistulae) noted at the hernia repair site
	and occurring within the first three months of the ventral hernia
	repair.
	2. Incidence of other early post-operative
	complications (e.g. ileus, bowel obstruction, fistula) occurring
	within the first three months of the ventral hernia repair.
	Secondary endpoints:

	 
	Incidence of late post-operative surgical site occurrences or wound related events (e.g. ileus, deep or superficial wound infection, seroma, hematoma, wound
	dehiscence, skin necrosis, fistulae, bulging) noted at the
	hernia repair site and occurring > 3 months after index
	surgery.
	2. Incidence of other late post-operative
	complications (e.g. ileus, bowel obstruction, fistula)
	occurring > 3 months after index surgery.
	3. Patient Reported Outcomes (QoL and pain assessments).
	4. True hernia recurrence at the site of surgery at
	post-operative day 90 and months 12 and 24 months.
Clinic Visits	Baseline, hospital stay (admission, day of surgery, day of discharge),
	30 days, 90 days, 12 months, 24 months.

Time and Events Schedule

Assessments	Baseline Visit (BV)	Hospital Stay			Post-operative Visits			
		Admission	Day of Surgery (DOS)	Day of Discharge (DOD)	Day 30 (±2wks)	Day 90 (±2wks)	Month 12 (±4wks)	Month 24 (±4wks)
Informed Consent	X							
I/E Criteria	X		X					
Medical History	X		X					
Physical Exam	X		X					
Hospitalization & Perioperative Information		X	X	X				
Surgeon Assessment of Mesh			X					
Surgical Site Assessment *				X	X	X	X	X
Ventral Hernia Assessment	X**				X	X	X	X
Pain Visual Analogue Scale					X	X	X	X
QOL scales	X				X	X	X	X
Subject/Surgeon Satisfaction					X	X	X	X
Adverse Events			X	X	X	X	X	X

^{*} Surgical site assessment is intended to document any surgical site occurrences of wound related events noted at the hernia repair site.

^{**} Baseline ventral hernia assessment is intended to estimate the actual hernia defect size.

LIST OF TABLES

Table 1: Adverse Event Severity

LIST OF FIGURES

Figure 1: Image of OviTex 1S Permanent RBS

Investigational Plan OviTex®

Page 9

v2.0_15-Jun-2017

Glossary of Terms and Abbreviations

AE Adverse Event

ASA American Society of Anesthesiologists

BV Baseline Visit

BMI Body Mass Index

CFR Code of Federal Regulation

Cm Centimeter

COPD Congestive Obstructive Pulmonary Disorder CO2 Carbon Dioxide

CRF Case Report Form

CT Computerized Tomography

CV Curriculum Vitae
DOS Day of Surgery

EBL Estimated Blood Loss

ECM Extracellular Matrix

EQ-5D EuroQol 5 Dimension

FDA U.S. Food and Drug Administration

GAGs Glycosaminoglycans

GCP Good Clinical Practice

HerQLes Hernia-Related Quality-of-Life Survey to Assess Abdominal Wall Function

ICH International Conference on Harmonization

I/E Inclusion/Exclusion

IRB Institutional Review Board

ISO International Organization for Standardization

MEC Medical Events Committee

Mm Millimeter

OTC Over the Counter
OTM Ovine Tissue Matrix

OR Operating Room

PE Physical Exam

POD Post Operative Day(s)
PTFE Polytetrafluoroethylene

QoL Quality of Life

RBS Reinforced BioScaffold
SAE Serious Adverse Event
SSI Surgical Site Infection

UADE Unanticipated Adverse Device Effect

VAS Visual Analogue Scale

WKS Weeks

STUDY OVERVIEW

A baseline visit will be performed prior to the ventral hernia repair and will include assessment of the subject's medical history, physical exam and pre-operative instructions. The subjects will also complete baseline Quality of Life (QOL) Surveys, one of which will be a disease specific assessment (HerQLes) and the other a standard measure of health outcomes (EQ-5D)

On the day of surgery, repair of the ventral hernia will occur using OviTex® Permanent 1S reinforced bioscaffold to reinforce the repaired hernia site. Perioperative data will be collected, including the anatomical placement of the mesh and fixation methods. During the course of hospitalization the patient will be assessed for incidence of early post-operative surgical site wound events and complications including the nature and severity of the complications, all necessary medical interventions and/or re-operations.

On the day of hospital discharge, surgical site occurrences or wound related events (e.g. infections, hematomas, seromas, wound dehiscence) noted at the hernia repair site and the occurrence of other early post-operative complications (e.g. ileus, bowel obstruction, fistulae) will be assessed.

At post-operative days 30 and 90, surgical site occurrences or wound related events (e.g. infections, hematomas, seromas, wound dehiscence) noted at the hernia repair site will be assessed. If a clinically significant hernia is suspected e.g. bulging noted at the hernia site, it will be confirmed via diagnostic imaging with a CT scan. The occurrence of other post-operative complications (e.g. ileus, bowel obstruction, fistulae) will be also assessed. Disease specific and general Quality of Life (QoL) surveys (HerQLes and EQ-5D), a pain scale and a subject/surgeon satisfaction assessment will also be administered.

At post-operative months 12 and 24, late surgical site occurrences or wound related events (e.g. infections, hematomas, seromas, wound dehiscence, bulging) noted at the hernia repair site will be assessed. If a clinically significant hernia is suspected e.g. bulging noted at the hernia site, it will be confirmed via diagnostic imaging with a CT scan. The occurrence of other late post-operative complications (e.g. ileus, bowel obstruction, fistulae) will also be assessed. Disease specific and general Quality of Life (QoL) surveys (HerQLes and EQ-5D), a pain scale and a subject/surgeon satisfaction assessment will also be administered.

Concomitant treatments, surgeries and Adverse Events (AEs) will be collected throughout the study period. Subject safety will be monitored throughout the study period; from the Day of Surgery through the Month 24 visit. All AEs, UADEs and SAEs that occur from the day of surgery through the Month 24 visit will be reported in the CRF. In addition to notation in the CRF, all SAEs will also require completion of a separate reporting form for submission to the Sponsor through Day 90. Following the Day 90 visit, only SAEs considered by the investigator to be "Related or "Possibly Related" to the study product will require completion of the additional reporting form for submission to the Sponsor. Conversely, following the Day 90 visit, it will no longer be necessary to complete the separate reporting form for those SAEs that the investigator determines to be "Unrelated" to the OviTex mesh.

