It is hypothesized that the use of OviTex® Permanent 1S reinforced bioscaffold in abdominal hernia repair (in comparable subjects) will result in less seroma formation, the same percentage or fewer infections and fewer surgical repair related secondary procedures such as fluid aspirations or wound debridement. In addition, the use of OviTex® Permanent 1S reinforced bioscaffold is expected to result in a similar or lower rate of true recurrent herniations as reported for comparable prospectively studied subjects in the literature treated with other implants. [30-33] Surgical procedure related outcomes tend to occur within the first three months after surgery, and the recurrence of a hernia may occur at any point in time after treatment. This study focuses on the surgical outcomes over the first 3 months and continues for a total of 24 months to capture the longer-term incidence of hernia recurrences.

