2 OBJECTIVES, HYPOTHESES, PRIMARY AND SECONDARY ENDPOINTS

2.1 OBJECTIVES

The study is designed to demonstrate that, in subjects with comparable characteristics, the use of OviTex® Permanent 1S reinforced bioscaffold in ventral hernias leads to the same or lower percentage of early post-operative complications and true hernia occurrences as compared to prospective reports in the literature for either synthetic or biological meshes.

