2.2.2 Secondary Endpoints

- Incidence of late post-operative surgical site occurrences or wound related events (e.g. ileus, deep or superficial wound infection, seroma, hematoma, wound dehiscence, skin necrosis, fistulae, bulging) noted at the hernia repair site and occurring > 3 months after index surgery.
- 2. Incidence of other late post-operative complications (e.g. ileus, bowel obstruction, fistula) occurring > 3 months after index surgery.
- 3. Patient Reported Outcomes (QoL and pain assessments).
- 4. True hernia recurrence at the site of surgery at post-operative day 90 and 12 and 24 months.

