2.3.1 Rationale for the OviTex® Permanent 1S reinforced bioscaffold study

The purpose of the OviTex® Permanent 1S reinforced bioscaffold Study is to provide prospective data on the early post- operative clinical course and the true hernia recurrence rates in the repair of ventral hernias. Data relating to subjects with similar baseline characteristics will be correlated and compared to (prospective) published data where applicable.

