3.2.3 Discharge

On the day of hospital discharge, the following will be collected:

- Length of Stay, including number of days hospitalized prior to repair and following surgery, the number of days in ICU, step down and regular ward.
- Number of drains still in place, drain volume and duration.
- Any early surgical site occurrences (infections, seroma, hematoma, wound dehiscence)
 or wound related events noted at the hernia repair site.
- Any other early post-operative complications (ileus, fistulae).

3.3 POST-OPERATIVE DAYS 30 AND 90

At post-operative days 30 and 90, the following procedures will be completed:

- Number of drains still in place, drain volume and duration.
- Assessment of any surgical site occurrences or wound related events (infections, seromas, hematoma, wound dehiscence) noted at the hernia repair site.
- A relevant physical examination to evaluate hernia repair. If there is any suspicion of a recurrent hernia e.g. bulging noted at the repair site, an abdominal CT scan will be performed to confirm the clinical diagnosis. If it is determined that it is clinically necessary to repair the hernia recurrence during the study period, those subjects will complete their participation in the study at the time of that repair
- Assessment of any other post-operative complications (ileus, fistulae).
- Assessment of disease specific and general Quality of Life (QoL) surveys e.g. EQ-5D and HerQLes, (See Appendix 1).
- Subject and Surgeon satisfaction assessment of hernia repair (See Appendix 5).
- Subject assessment of post-operative pain as measured by the Pain Visual Analog Scale ((VAS) See Appendix 5).

3.4 POST-OPERATIVE MONTHS 12 AND 24

The following activities will be performed at months 12 and 24 of Study period visit:

- Assessment of any late surgical site occurrences or wound related events (e.g. infections, seromas, hematoma, wound dehiscence, bulging) noted at the hernia repair site.
- A relevant physical examination to evaluate hernia repair. If there is any suspicion of a recurrent hernia e.g. bulging noted at the repair site, an abdominal CT scan will be performed to confirm the clinical diagnosis. If it is determined that it is clinically necessary to repair the hernia recurrence during the study period, those subjects will complete their participation in the study at the time of that repair.

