7.2 STATISTICAL METHODS

Statistical methods will be carried out in accordance with the Statistical Analysis Plan (SAP) developed for this study.

The majority of data will be expressed as descriptive statistics. A p-value of less than or equal to 0.05 will be considered statistically significant. Any confidence bounds will show two-sided 95% confidence interval limits. Categorical variables will be summarized by number and percent. Continuous variables will be summarized by total number (N), mean, standard deviation, median, min and max. It is anticipated that the data will be evaluated using standard parametric and non-parametric procedures. Analyses of particular interest will be:

1. Correlation of rate of surgical site wound infection to SSI wound classification, number of previous repairs and pre-morbid conditions.

- 2. Correlation of surgical site occurrences or wound related events to re-herniation, BMI, number of previous abdominal.
- 3. Correlation of number of previous repairs with true hernia recurrence
- 4. Correlation of a visible bulge at hernia repair site with true hernia recurrence
- 5. Correlation of subject abdominal wall function and QoL with bulging at the hernia repair site and hernia recurrence rates.

The primary and secondary endpoints of this study will be also be compared to the clinical outcomes reported for other prospective studies in the literature. The results will be compared for the group as a whole, and, if the numbers will allow this, for subgroups of subjects exhibiting similar baseline characteristics, such as size of the hernia, co-morbid conditions, number of previous abdominal procedures etc.

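### The literature comparison of recurrence sets no condition on how or when comparator studies ascertained it, so an apparent difference could come from ascertainment rather than the device

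*Combined protocol and SAP*

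**What the plan says.** Recurrence is the fourth secondary endpoint: "True hernia recurrence at the site of surgery at post-operative day 90 and 12 and 24 months" (section 2.2.2). The Time and Events Schedule has a ventral hernia assessment at each of the four post-operative visits and no imaging row. CT depends on suspicion, and the trigger is worded in two ways:

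- Study Overview: where the suspected hernia is clinically significant, for instance with bulging at the site, "it will be confirmed via diagnostic imaging with a CT scan".
- Section 3.3, repeated in 3.4 for months 12 and 24: "If there is any suspicion of a recurrent hernia e.g. bulging noted at the repair site, an abdominal CT scan will be performed".

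The yardstick is external. Section 2.1 aims to show that the device "leads to the same or lower percentage of early post-operative complications and true hernia occurrences as compared to prospective reports in the literature". Section 1.2 expects a "similar or lower rate of true recurrent herniations as reported for comparable prospectively studied subjects in the literature".

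Three places say what makes a comparison admissible:

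- Section 2.3.1: "Data relating to subjects with similar baseline characteristics will be correlated and compared to (prospective) published data where applicable".
- Section 7.2: primary and secondary endpoints are to be "compared to the clinical outcomes reported for other prospective studies in the literature". The whole group comes first; subgroups alike at baseline (for example in hernia size or co-morbidity) follow only if numbers permit.
- Section 2.5: the interim look at comparability concerns baseline characteristics.

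None of them mentions the definition of recurrence, the detection method or the time of assessment. Section 7.2 refers to a separate SAP, whose text is not part of the combined file.

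**The concern.** With one arm and no concurrent control, the recurrence conclusion rests entirely on the external comparison. A recurrence percentage depends on the device and the patients, but also on how hard and how long one looks and on what counts as a case. Similar baseline characteristics deal with the patients only, and the whole-group comparison does not secure even that.

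Three mismatches are possible under the rule as written. A comparator may have imaged everyone. It may have counted clinical recurrences without CT confirmation. Or it may have assessed recurrence at a different time. In each case a same-or-lower finding, or its absence, could arise without any difference between devices. Recurrence is secondary, but it appears in the objective (2.1) and the design statement (2.3), and section 1.2 gives it as the reason for following subjects to 24 months.

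**Working it through.** **No figure to reproduce.** Section 7.1 describes the 100 subjects as a convenience sample, without a benchmark rate, margin or power. Section 1.1 gives a published recurrence range of 2.7% to 62% and selects no value from it.

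**Ascertainment set beside the comparator rule.**

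| Feature | This trial | Required of comparators |
|---|---|---|
| Design | Prospective, single arm | Prospective |
| Baseline profile | As enrolled | Similar, for subgroups if numbers permit; whole group unmatched |
| Detection | Examination, CT on suspicion | Not mentioned |
| Meaning of a true recurrence | No operational definition | Not mentioned |
| Time points | Day 90, months 12 and 24 | Not mentioned |

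The reports cited in section 1.2 as comparable prospective experience (references 30 to 33) show that the rule lets unlike studies in. By their titles, two concern inguinal hernia; one of these is an early report and the other a 3-year study. Their titles do not say how recurrence was detected.

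**Illustration of missed recurrences.** Let s be the share of recurrences this trial detects out of those the comparator's method would count. The documents give no value for s; I assume 0.6 to 1.0, where 1.0 means no difference in detection.

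Observed rate = true rate × s

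- True 15%: 0.15 × 0.6 = 9%; 0.15 × 1.0 = 15%. Apparent advantage 0 to 6 points.
- True 10%: 0.10 × 0.6 = 6%; 0.10 × 1.0 = 10%. Apparent advantage 0 to 4 points.

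**What that does to a conclusion.** Take 100 evaluable subjects (no loss to follow-up, an assumption) and a fixed comparator rate of 20% (an assumed value inside the 2.7% to 62% range). The count X is binomial with n = 100 and probability s × true rate. The observed rate is at or below the comparator's if X ≤ 20. The exact two-sided 95% interval lies wholly below 20% if X ≤ 11.

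| s | True rate 20%: observed at or below 20% | True rate 20%: interval wholly below 20% | True rate 25%: observed at or below 20% |
|---|---|---|---|
| 1.0 | 55.9% | 1.3% | 14.9% |
| 0.8 | 88.8% | 10.6% | 55.9% |
| 0.7 | 96.4% | 24.1% | 78.8% |
| 0.6 | 99.3% | 45.4% | 93.4% |

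In the first two probability columns the device equals the comparator; in the last it is worse by 5 points.

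**What the illustration leaves out.** It models missed recurrences only. Suspected cases that CT does not confirm are a separate matter: some would be false positives, and removing them makes the count more accurate. Against a comparator that counted clinical diagnoses, it would still make the two rates unlike. Differences in time point are not modelled either.

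**The case against.** The strongest reply is that no bias has been shown. The documents do not describe any comparator's detection method. If comparators also examined patients and imaged on suspicion, s is 1 and nothing in the detection method favours this trial. The direction is open too: four scheduled assessments with CT on suspicion may find more than a comparator with sparse or passive follow-up, which would count against the device. This stands. A reader might infer that the trial's recurrence rate is lower by construction; the documents do not support that.

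A reader might also infer that only recurrences suspected on examination and then confirmed by CT will be counted. The text says CT is to confirm the clinical diagnosis, but states no counting rule. Section 6.3.1 also makes recurrent hernia a recordable adverse event, and adverse events are collected through month 24, so a recurrence found by another route would at least be recorded.

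Nor are comparators chosen on baseline characteristics alone: they must also be prospective.

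Three further points bear on weight. Recurrence is a secondary endpoint, and the analysis is mainly descriptive. Section 7.2 already plans to correlate a visible bulge with true recurrence, which touches the gap between suspicion and confirmation. And the separate SAP may contain a comparator rule. These limit the importance of the point, but leave a stated objective resting on a rule that is silent about ascertainment. Because comparator methods are unknown, the plan should require them to be recorded before a conclusion is drawn.

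**Conclusion.** The point holds as a gap in the comparator rule. As written, section 7.2 permits a same-or-lower statement about recurrence against studies that defined, sought or timed it differently. Confounding of device with ascertainment is possible, not demonstrated; its direction and size depend on comparator methods the documents do not give. Under the assumed s of 0.6 to 1.0, the apparent advantage runs from 0 to 6 points at a true 15% and from 0 to 4 points at a true 10%. The probabilities further assume 100 evaluable subjects and a fixed comparator rate. If s exceeds 1, the distortion runs against the device.

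Separately, the trigger wordings in the Study Overview and in sections 3.3 and 3.4 set different thresholds for imaging, and the threshold affects the count. They must be reconciled; which one is right is not a question for this review.

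This is a cheap improvement. It should not be read as a call for routine imaging.

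**What to change.** In section 7.2 or the SAP:

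1. State that the endpoint is recurrence found by examination with CT on suspicion, and give the counting rule.
2. For every comparator study, tabulate the definition of recurrence, the detection method and the follow-up time.
3. Restrict any same-or-lower statement on recurrence to comparators with similar examination-led detection and a comparable time point. Show the others separately and descriptively.
4. At each visit, report the numbers examined, clinically suspected and CT-confirmed. First confirm that the case report form captures suspicion: no section lists it as a data item, and bulging is named among the assessed site events only at months 12 and 24.
5. Reconcile the two imaging-trigger wordings.

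If the separate SAP already contains such a rule, a cross-reference from section 7.2 is enough for that item.

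The cost is SAP wording, a few columns in the comparator table and possibly one form field. No extra procedure for subjects is needed. The downside is fewer eligible comparator studies; if none qualifies, recurrence is reported descriptively without a same-or-lower conclusion.
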